11.1.3.3 QT Interval Prolongation

Acquired long QT syndrome can lead to life-threatening ventricular arrhythmias, particularly torsades de pointes. Risk factors for occurrence of arrhythmia include hypokalemia, hypomagnesemia, bradycardia, and concurrent use of multiple medications that prolong the QTc(F) interval. In vivo observations of QTc(F) prolongation in association with use of tesevatinib have been observed, including Grade 3 QTc(F) prolongation. However, the lack of a clearly discernible pattern to such occurrence makes prediction of individual subject risk difficult. Therefore, the following are recommended:

- Tesevatinib should be administered to subjects who have normal serum potassium and serum magnesium levels;
- Tesevatinib should not be administered to subjects with pathologic bradycardia;
- Medications with potential for QTc(F) prolongation should not be used concurrently or started within 24 hours of tesevatinib administration.

Subjects should be carefully monitored for symptoms of arrhythmia (i.e., dyspnea, chest pain or tightness, palpitations, dizziness) and for episodes of syncope. An ECG should be obtained if these symptoms occur. In addition, serum potassium and magnesium must be maintained within the normal range¹⁶ and may require additional monitoring or adjustment if subjects develop diarrhea.

11.1.3.4 Response to QTc(F) Interval Prolongation

The following guidelines should be used in the management of QTc(F) prolongation. Subjects will have ECGs performed at times designated by the protocol.

If the QTc(F) interval increases to an absolute value of ≥ 60 msec above Cycle 1 Day 1 (predose on Day 1) but < 500 msec and the subject is asymptomatic (does not have palpitations, dizziness, syncope, orthostatic hypotension, or a significant ventricular arrhythmia on ECG), the following actions should be taken:

- Re-check and confirm concomitant medications for any medications that may be contributing to QTc(F) prolongation. Consult medical monitor for discontinuation of any medication found;
- Check electrolytes, especially magnesium and potassium; correct abnormalities as clinically indicated;
- Obtain blood sample (plasma) for PK analysis.

If the QTc(F) interval increases to an absolute value of ≥ 500 msec at any evaluation and if the subject is asymptomatic (does not have palpitations, dizziness, syncope, orthostatic hypotension, or a significant ventricular arrhythmia on ECG), then the following actions should be taken:

- Consult with medical monitor;
- Hold study drug;
- Re-check and confirm concomitant medications for any medications that may be contributing to QTc(F) prolongation. Consult medical monitor for discontinuation of any medication found;
- Check electrolytes, especially magnesium and potassium; correct abnormalities as clinically indicated;
- Obtain blood sample (plasma) for PK analysis;
- Contact medical monitor to discuss appropriate management;
- **QTc(F)**: When QTc(F) is within 30 msec of Cycle 1 Day 1 or ≤ 470 msec (whichever is lower), then study drug may be restarted with one dose level reduction;
- Following dose reduction and resumption of study drug treatment, ECGs must be repeated weekly for 2 weeks, then on Day 1 of each cycle per protocol following restart of study drug;
- Study drug may be restarted at the pre-event dose level if QTc(F) values of ≥ 500 msec are not confirmed by the central lab and if there is no evidence of drug-related abnormal ECG findings. This may be done as soon as the data are confirmed.

If the QTc(F) interval increases to an absolute value of ≥ 500 msec at any evaluation, and if the subject is or has recently been symptomatic (has palpitations, dizziness, syncope, orthostatic hypotension, a significant ventricular arrhythmia on ECG), then the following actions should be taken:

- Consult with medical monitor;
- The subject should be hospitalized and undergo a thorough cardiology evaluation;
- Do not dose with study drug again;
- Obtain blood (plasma) for PK sample;
- Check electrolytes especially magnesium and potassium; correct abnormalities as clinically indicated;
- ECGs should be monitored until the QTc(F) returns to within 30 msec above the average Cycle 1 Day 1 value or ≤ 470 msec.

Study drug should be permanently discontinued if the cardiac/electrophysiology evaluation confirms that symptoms are the consequence of a drug-induced QTc(F) interval prolongation.

However, if the subject has objective tumor response, consideration will be given to continuing treatment with tesevatinib at a reduced dose after discussion with the medical monitor.

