Safety assessments	
The National Cancer Institute Common Terminology Criteria for Adverse Events (NCI CTCAE; Version 4.03 - www.hrc.govt.nz/sites/default/files/CTCAE%20manual%20-%20DMCC.pdf) will be used for grading toxicities. Safety assessments will include adverse events (AEs), serious adverse events (SAEs), physical examinations (PEs), vital sign measurements, clinical safety laboratory evaluations (hematology, serum chemistry, and urinalysis), ECOG scores, and ECGs.
 
The AE reporting period for a subject enrolled in the study begins when the subject provides informed consent and is continued through 30 days after the last dose of study drug or until start of new treatment. All AEs that occur in enrolled subjects during the AE reporting period specified in the protocol must be recorded, regardless of the relationship of the AE to study drug. Any known untoward event that occurs beyond the AE reporting period that the investigator assesses as possibly related to tesevatinib should be reported to Kadmon.
 
Vital sign measurements, including sitting blood pressure, pulse rate, respiratory rate, and temperature will be monitored throughout the study.
 
If \geq Grade 3 CTCAE AEs occur that are determined to be at least possibly related to study drug (with the exception of asymptomatic Grade 3 elevations of amylase or lipase, Grade 3 elevation of alkaline phosphatase in a subject known to have bone metastases, Grade 3 elevation of glucose in a subject receiving systemic corticosteroids, Grade 3 creatine phosphokinase [CPK] elevation in the absence of muscle symptoms, or Grade 3 sodium values \geq 126 mmol/L in a subject with diarrhea), tesevatinib will be withheld until all drug-related toxicities have resolved to \leq Grade 1.
 
If the QTc(F) interval increases to the level of \geq 500 msec study drug should be withheld and appropriate investigations undertaken.

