9.1.7 Pregnancy Test

Urine pregnancy tests are to be performed for females of childbearing potential. Positive urine tests are to be confirmed with serum pregnancy testing.

9.1.8 12-Lead Electrocardiogram (ECG)

Supine 12-Lead ECGs will be performed at screening; Days 1, 7 and 14 of Cycle 1; on Day 1 of Cycles 2 and Day 1 of each Cycle including at End of Study Drug Treatment visit. Assessment to

be performed at predose, and once within 4 – 8 hours postdose for Days 1, 7 and 14 of Cycle 1. ECGs are to be performed before any blood sample collection when possible.

ECGs are to be repeated three times consecutively within 30 minutes (must have an interval of at least 1–2 minutes between ECGs).

During the study, all ECGs will be digitally analyzed by a validated ECG laboratory. This central vendor will place ECG machines at sites under contract with Kadmon. ECGs will be transmitted electronically to the central vendor for analysis. Reports, including clinical alerts resulting from the analysis of the ECGs, will be provided back to sites. Sites will be trained on the use of the ECG machines, and instructions for performing ECG assessments will be provided in the ECG manual.

The QT interval will be corrected using Fridericia's formula¹:

$$QT_F = \frac{QT}{RR^{1/3}}$$

Refer to Appendix C for sample calculation.

Prior to enrollment, all subjects must demonstrate an average screening QTc(F) value of ≤ 470 msec by central digital analysis. Immediate clinical management of subjects will initially be based on results of machine-read ECGs at the sites. However, the central digital analysis will prevail as it becomes available. In addition, the central digital analysis will be used for any AE and SAE documentation.

An increase in QTc(F) interval (by central digital analysis) to a value > 60 msec above Cycle 1 Day 1 or to the level of ≥ 500 msec requires further monitoring. After collection of a PK blood sample and discussion with the medical monitor (if ≥ 500 msec) on appropriate management, the subject may be removed from the trial (see guidelines in Section 11.1.3.3).

Abnormalities in the ECG that lead to a change in subject management (e.g. requirement for additional medication or monitoring) or result in clinical signs and symptoms are considered clinically significant for the purposes of this study and will be recorded on the AE eCRF. If ECG

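### For symptomatic QTcF of 500 msec or more, Protocol 11.1.3.4 bars any further dosing and then allows continued dosing to be considered in responders

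*Protocol*

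**What the plan says.** Protocol Section 11.1.3.4 divides QTcF of 500 msec or more into an asymptomatic and a symptomatic branch. The symptomatic branch applies when the threshold is reached "at any evaluation, and if the subject is or has recently been symptomatic". It makes three statements about further dosing:

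1. A bullet in the action list, with no condition: "Do not dose with study drug again".
2. A sentence after the list: "Study drug should be permanently discontinued if the cardiac/electrophysiology evaluation confirms that symptoms are the consequence of a drug-induced QTc(F) interval prolongation".
3. A closing sentence, opening with However and requiring medical monitor input: "if the subject has objective tumor response, consideration will be given to continuing treatment with tesevatinib at a reduced dose".

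The asymptomatic branch is worded differently. It tells the site to hold the drug, gives a QTcF recovery criterion, and says "then study drug may be restarted with one dose level reduction", followed by repeat ECGs.

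Two other places deal with the same threshold without splitting it by symptoms. The Synopsis (Safety assessments) says "study drug should be withheld and appropriate investigations undertaken". Section 9.1.8 (12-Lead ECG) says that, after a PK sample and discussion with the medical monitor, "the subject may be removed from the trial (see guidelines in Section 11.1.3.3"). Section 12.3.1 also refers the reader to 11.1.3.3 for managing QTcF prolongation.

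**The concern.** A site facing this event needs one instruction. Statement 1 rules out further study drug, while statement 3 keeps it open for a subject whose tumor has responded. An investigator who never re-doses and one who, with the monitor, re-doses a responder can both cite the same section. The Protocol itself describes acquired long QT as a route to life-threatening arrhythmia and says that individual risk is hard to predict (Section 11.1.3.3), so the instruction has to be clear even if it is seldom used.

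There is a small effect on reporting. Which sentence is followed decides whether such a subject appears in the SAP safety outputs as a treatment discontinuation or as a dose modification, and it changes that subject's exposure.

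**Working it through.** The Protocol gives no figure to reproduce on this point. The check is to see what each statement requires in each situation the branch can produce.

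| Subject | 1. Bullet | 2. Discontinuation sentence | 3. Responder exception | Result |
|---|---|---|---|---|
| No response, cause not confirmed | No further drug | Silent | Not applicable | Bullet alone speaks |
| No response, cause confirmed | No further drug | Discontinue | Not applicable | Consistent |
| Response, cause not confirmed | No further drug | Silent | Reduced dose may be considered | 3 conflicts with 1 |
| Response, cause confirmed | No further drug | Discontinue | Not stated whether it reaches this case | If it does, 3 conflicts with 1 and 2 |

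The clash is therefore confined to responders. If statement 1 is absolute, statement 2 is redundant in every row and statement 3 can never take effect. If statement 3 can take effect, statement 1 is not absolute. In the last row the text does not say whether the exception overrides a confirmed drug-induced cause or covers only unconfirmed cases.

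**Does another section settle it?** No. The Synopsis says to withhold and investigate. Section 9.1.8 allows removal from the trial. Sections 9.1.8 and 12.3.1 both point to 11.1.3.3, which covers risk factors, electrolytes and symptom monitoring but has no rule for responding to a QTcF of 500 msec or more. Those rules are in 11.1.3.4.

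**How often might it arise?** The branch needs the threshold and symptoms together.

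- Threshold, 300 mg daily NSCLC study (XL647-203; Synopsis and Section 5.1.2): 2 of 41 centrally confirmed above 500 msec. 2/41 = 4.9%; 0.049 × 60 = 2.9 subjects.
- Threshold, all centrally reviewed subjects (Section 5.2.1): 2 of 178. 2/178 = 1.1%; 60 × 2/178 = 0.7 subjects. This pool includes all 41 from XL647-203, so these may be the same two people.
- Symptoms: the Protocol says every subject with QTc prolongation in tesevatinib studies was asymptomatic. Section 5.2.1 reports no associated clinical findings among 169 treated cancer subjects. Reading that as 0 of 169, the one-sided 95% upper bound is 1 − 0.05^(1/169) = 1.8%, and 0.018 × 60 is about 1 subject.

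The scaling assumes that all 60 places are filled and that earlier subjects resemble these. The 169 had mixed doses and schedules.

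**The case against.** **The order of the text helps.** The bullets can be read as immediate actions, the next sentence as the outcome of the cardiac evaluation, and the However sentence as an exception. On that reading the bullet is a hold pending evaluation. This narrows the ambiguity but does not remove it. The asymptomatic branch uses plain hold wording and states when dosing may resume, whereas the symptomatic bullet is worded as permanent. Even if the bullet is only a hold, the case of a responder with a confirmed drug-induced cause stays open.

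**The medical monitor is a gate.** The first bullet requires consultation, the exception applies only after discussion, and Section 15.3.11.2 says the safety medical monitor can be reached at all times. That stands. A reader might infer that sites are free to go opposite ways on their own, and the documents do not support that. What remains is that neither the site nor the monitor is told which sentence governs.

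**Three mutually incompatible instructions.** A reader might infer this by taking statement 2 to mean that the drug is stopped solely when the cause is confirmed. The sentence gives a condition for stopping and does not say it is the sole one. A site can obey statements 1 and 2 together, so they are redundant or in tension. The contradiction is between 1 and 3, and possibly between 2 and 3.

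**About 4 of 60 subjects.** A reader might scale the 12 of 169 Grade 3 values in Section 5.2.1 (7.1%; 4.3 of 60). Those are machine reads, over which central analysis prevails under Section 9.1.8. They had no associated clinical findings, so they would fall in the asymptomatic branch. The figure should not be used here.

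**Conclusion.** The point holds as an internal contradiction in one safety rule. The unconditional bar and the responder exception cannot both have effect, the discontinuation sentence between them is redundant if the bar is absolute, and responders with a confirmed drug-induced cause are left unaddressed. No other section resolves it.

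The number affected should be small. Earlier central readings suggest roughly 0.7 to 2.9 of 60 subjects above 500 msec, and earlier experience contains no symptomatic case. One caution is my own inference: entry to the branch counts dizziness and orthostatic hypotension, does not define how recent a symptom must be, and does not require it to be attributed to QTcF. In subjects with CNS disease and a drug that causes diarrhea, it could be entered more often than past data suggest.

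A reader might also infer that the efficacy results are at risk. The documents do not support that. The SAP plans descriptive summaries of all treated subjects with no formal testing, and the exception concerns subjects who have already responded. At most, a rare subject's exposure, duration or discontinuation category changes. The reason to act is subject safety and clarity, not bias in an estimate.

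**What to change.** The sponsor should reconcile the three statements in the symptomatic part of Section 11.1.3.4 into a single instruction. It should say which statement prevails, whether the responder exception applies when a drug-induced cause has been confirmed, and who makes the decision. The references to Section 11.1.3.3 in Sections 9.1.8 and 12.3.1 should be changed to 11.1.3.4, where the response rules are, and the Synopsis and Section 9.1.8 wording checked against the reconciled text.

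No view is given on which rule is clinically right. The cost is amendment wording; sample size, assessments and planned analyses are unaffected.

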5.2 Safety Profile of Tesevatinib

5.2.1 Tesevatinib

AEs that have been associated with tesevatinib include the following: diarrhea, skin rash, QTc(F) prolongation, elevated serum creatinine, elevated serum amylase, and interstitial lung disease (see Warnings, Precautions, and Management in Section 11.1.3).

Diarrhea: Diarrhea is an expected AE for agents like tesevatinib that have significant EGFR inhibitor activity. Grade 3 diarrhea was the dose-limiting toxicity (DLT) for both the 5 days out of 14 days schedule of tesevatinib in study XL647-001 as well as for the daily dosing of tesevatinib in the KD019-204 study of tesevatinib in patients with metastatic breast cancer. At

doses below those that cause DLT, diarrhea has generally been manageable with anti-diarrheal medications such as loperamide.

Skin Rash: Acneiform skin rash is an expected AE for agents like tesevatinib that have significant EGFR inhibitor activity. The rash characteristically involves the chest and face. Paronychia involvement, although characteristic of EGFR inhibitors, has not been seen in tesevatinib studies.

QTc(F) Prolongation: In clinical trials of tesevatinib, cases of QTc(F) prolongation have been observed.

Common Terminology Criteria for Adverse Events (CTCAE v4.03) was used to assign the severity grade for QTc(F) AEs and the criteria for each grade are presented below.

	Grade 1	Grade 2	Grade 3	Grade 4
ProlongedQTc(F) interval	> 450–470 msec	> 470–500 msec or ≥ 60 msec above Cycle 1 Day 1	> 500 msec	> 500 msec with life threatening signs or symptoms; torsades de pointes

In the 169 subjects with malignancies treated in 4 uncontrolled studies, the majority of whom had advanced, metastatic non-small cell lung cancer, 33 (20%) were found to have QT prolongation based on machine read ECGs at some time during treatment that met the CTCAE v4.03 definition of an AE: Grade 1 [7 (4%) subjects], Grade 2 [14 (8%) subjects], and Grade 3 [12 (7%) subjects]. The majority of these subjects received ≥ 300 mg daily or 350 mg given for 5 days with 9 days off. There were no clinical findings associated with the ECG changes. There were no reports of QTc(F) prolongation in 32 healthy volunteer subjects who received a single 300 mg dose of tesevatinib.

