 13. Has marked prolongation of QTc(F) interval at screening or Cycle 1 Day 1 (QTc[F] interval > 470 msec) using the Fridericia method of correction for heart rate.
 14. Gastrointestinal (GI) condition that interferes with drug absorption.
 15. Non-malignant neurological disease that would interfere with evaluation of symptoms or signs attributed to brain metastases.

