9.2.13 Unscheduled/AE Resolution Visits: To Occur as Needed

If additional visits are needed (e.g. for resolution of an AE), the following procedures and evaluations may be performed as needed:

- Complete physical examination, including weight;
- Vital sign measurements (sitting blood pressure, pulse, respiratory rate, temperature);
- ECOG Performance status

- Hematology, serum chemistry and urinalysis;
- Urine pregnancy test, if applicable (positive results to be confirmed by serum pregnancy testing);
- Supine 12-Lead ECG (repeat three times consecutively within 30 minutes [must have an interval of at least 1-2 minutes between ECGs];
- Tesevatinib administration (if appropriate)
- AE assessment;
- Concomitant medications;
- Perform drug accountability, review subject diary, and collect old and dispense new study drug (if appropriate).

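### The rule for ending ECG monitoring after symptomatic QTcF of 500 msec or more can be met at Grade 2, mainly when baseline QTcF is 441–470 msec

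*Protocol*

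**What the plan says.** Protocol 11.1.3.4 has separate instructions for asymptomatic and symptomatic subjects whose QTcF reaches 500 msec or more.

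- **Symptomatic, ECG follow-up (last bullet):** "ECGs should be monitored until the QTc(F) returns to within 30 msec above the average Cycle 1 Day 1 value or ≤ 470 msec".
- **Symptomatic, other actions in the same list:** "The subject should be hospitalized and undergo a thorough cardiology evaluation", together with medical monitor consultation, a PK sample, electrolyte checks and an instruction not to dose again. A later sentence says that, for a subject with objective tumor response, "consideration will be given to continuing treatment with tesevatinib at a reduced dose after discussion with the medical monitor".
- **Asymptomatic, drug restart:** the same two values appear, but with a tie-break: "whichever is lower), then study drug may be restarted with one dose level reduction".

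Three other provisions bear on the result:

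- **Grading (Protocol 5.2.1):** Grade 2 is a QTcF above 470 and up to 500 msec "or ≥ 60 msec above Cycle 1 Day 1".
- **Monitoring trigger (Protocol 9.1.8):** an increase by central analysis "to a value > 60 msec above Cycle 1 Day 1 or to the level of ≥ 500 msec requires further monitoring".
- **Entry ceiling (Protocol 8.3, repeated in 8.5 and 8.7):** a subject is excluded who "Has marked prolongation of QTc(F) interval at screening or Cycle 1 Day 1 (QTc[F] interval > 470 msec". Baseline can therefore be as high as 470 msec.

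**The concern.** With no tie-break, the monitoring bullet is satisfied as soon as either limit is met. The more permissive of the two then governs, and which one that is depends on the subject's baseline. At a high baseline it is the 30 msec allowance. At a low baseline it is the fixed 470 msec.

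This is the protocol's most serious QT scenario: a value of 500 msec or more with palpitations, dizziness, syncope, orthostatic hypotension or a ventricular arrhythmia. A site that follows the bullet literally could end the specified ECGs while the subject still meets the protocol's definition of Grade 2 prolongation. At stake is the clarity of one safety instruction, not the interpretation of any efficacy or safety analysis.

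**Working it through.** The plan gives no figure to reproduce, so this is a direct check of thresholds.

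**Inputs.** Let b be Cycle 1 Day 1 QTcF and q the current QTcF, in whole msec. Entry requires b ≤ 470 (8.3, 8.5, 8.7). Grade 2 is 470 < q ≤ 500 or q − b ≥ 60 (5.2.1). The branch starts at q ≥ 500 (11.1.3.4).

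**Formulas.**

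1. Bullet as written: stop if q ≤ b + 30 or q ≤ 470. Highest stopping value = max(b + 30, 470).
2. Bullet with 9.1.8 also applied: the same, but the rise must be at most 60 and q below 500.
3. With the tie-break added: min(b + 30, 470).
4. With a Grade 1 condition added instead: q ≤ 470 and rise below 60, so min(470, b + 59).

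**Results (highest permitted stopping value, msec).**

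| b | As written (rise, grade) | With 9.1.8 (grade) | Tie-break added | Grade 1 condition added |
|---|---|---|---|---|
| 380 | 470 (+90, G2) | 440 (G2) | 410 | 439 |
| 400 | 470 (+70, G2) | 460 (G2) | 430 | 459 |
| 410 | 470 (+60, G2) | 470 (G2) | 440 | 469 |
| 420 | 470 (+50, G1) | 470 (G1) | 450 | 470 |
| 440 | 470 (+30, G1) | 470 (G1) | 470 | 470 |
| 450 | 480 (+30, G2) | 480 (G2) | 470 | 470 |
| 460 | 490 (+30, G2) | 490 (G2) | 470 | 470 |
| 470 | 500 (+30, G2) | 499 (G2) | 470 | 470 |

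**Reading the table.**

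- *b from 441 to 470.* As written, the limit runs from 441 + 30 = 471 to 470 + 30 = 500, all Grade 2. Section 9.1.8 does not help below 500 msec, because the rise is only 30. At b = 470 the stopping value equals the value that starts the branch; 9.1.8 lowers it by 1 msec, to 499.
- *b of 410 or lower.* As written, the 470 limit allows a rise of 470 − 410 = 60 or more. Section 9.1.8 calls for further monitoring above a rise of 60. With both followed, the only Grade 2 stopping value left is a rise of exactly 60.
- *b from 411 to 440.* The limit is 470 with a rise of 30 to 59, so it excludes Grade 2.

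A check at every whole msec, for b from 350 (an assumed floor) to 470 and q from 350 to 500, gave the same ranges for the bullet as written. It found no Grade 2 stop with the tie-break added, since that requires q ≤ 470 and a rise of at most 30.

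**The case against.** The case on the other side is that the protocol read as a whole leaves little exposure, and much of that stands.

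- **Other recovery rules.** Section 10.1.2 follows subjects withdrawn for toxicity to their Cycle 1 Day 1 status or Grade 1, and 15.3.8 also names Grade 1. It would be wrong to infer that nothing else points to recovery below Grade 2. But 10.1.2 applies to study withdrawal and can end if the event is otherwise explained, 15.3.8 also accepts a clinically satisfactory resolution, and neither is specific to ECGs. Section 9.2.13 permits ECGs at extra visits but does not require them: "If additional visits are needed (e.g. for resolution of an AE), the following procedures and evaluations may be performed as needed".
- **Re-dosing.** The sentence on tumor responders might suggest that drug could resume at Grade 2. The documents do not support that for a related event of Grade 3 or above: 11.1.2 and the Synopsis safety section hold drug until related toxicities are Grade 1 or lower.
- **Comparison with asymptomatic subjects.** A reader might infer that symptomatic subjects are held to a looser standard. The asymptomatic rule governs drug restart, whereas this bullet governs when ECG monitoring ends. The restart rule supplies consistent wording, but it is not a directly comparable limit.
- **Conflict with 9.1.8.** A reader might call the two sections contradictory. Both can be followed by continuing to monitor while the rise exceeds 60 msec. They should be aligned, but they are compatible. An asymptomatic subject at a rise of exactly 60 also falls under the first branch of 11.1.3.4, with medication review, electrolytes and a PK sample.
- **High baselines.** A subject within 30 msec of a 460 msec baseline has largely recovered, so some tolerance is defensible. That is a clinical argument for the allowance, but the stopping value is still Grade 2 by the protocol's own table.

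**Conclusion.** The point holds as a minor drafting gap in a safety instruction. It matters mainly for baselines of 441–470 msec, where no other ECG-specific text prevents the specified monitoring from ending at Grade 2, up to 30 msec above the 470 msec line (29 msec with 9.1.8 applied). For baselines of 410 msec or lower, what remains after 9.1.8 is a single boundary value.

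This rests on reading the bullet's conjunction literally and on the grading table in 5.2.1. The documents give no distribution of baseline QTcF, so the share of subjects in the affected range is unknown. Few subjects are likely to be involved. At most 60 enroll. The protocol reports that all QTc prolongation with this drug so far was asymptomatic, and that no serious events of torsades or ventricular tachycardia were received among more than 250 exposed subjects. Hospital care, cardiology review and the stop-dosing instruction reduce the risk further. No endpoint, sample size or analysis depends on it.

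**What to change.** In the last bullet of the symptomatic branch of Protocol 11.1.3.4, add *(whichever is lower)* after the 470 msec value. Monitoring then continues until QTcF is at or below min(b + 30, 470). This matches the wording of the restart rule and fits with 9.1.8.

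A smaller alternative keeps the bullet and adds the condition that QTcF prolongation is Grade 1 or less. That also removes every Grade 2 stop and avoids prolonging ECGs at ungraded values when baseline is low. For example, at b = 400 and q = 440 the tie-break would continue monitoring (limit 430), while the Grade 1 condition would allow it to end.

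The cost is a short protocol edit and a few extra ECGs in rare subjects. Under either version, subjects with a baseline near 470 msec bear most of it: the tolerance above baseline is 470 − 460 = 10 msec at 460 and zero at 470, so their monitoring may last longer.
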